9.4 STATISTICAL ANALYSES

9.4.1 GENERAL APPROACH

Continuous variables will be summarised with the number of observations (non-missing values), mean, standard deviation (SD), median, quartiles, minimum and maximum. The minimum and maximum values will be presented to the same number of decimal places as recorded in the raw data. The mean, median and SD will be presented to one more decimal place than the raw data. Categorical variables will be summarised with the number of observations and the numbers and percent from each category. Percentages will be rounded to one decimal place, with the denominator being the number of participants in the relevant population with non-missing data. No missing data will be imputed. If required, confidence intervals (CIs) will be two sided and will use 95% confidence levels. Any analyses requiring significance testing will use a two-sided test at the 5% significance level.

The inoculation baseline will be defined as the last available assessment prior to administration of the malaria challenge agent. The IMP baseline will be defined as the last available assessment prior to the administration of the IMP. Unscheduled visits will be excluded from summary tables. Assessments conducted at Early Termination will be excluded from summary tables.

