12.1.7 DEFINITIVE ANTIMALARIAL TREATMENT

All participants will receive compulsory definitive antimalarial treatment with Riamet® and/or other registered antimalarials if required on Day 24±24hrs, or earlier in the following cases:

- Insufficient parasite clearance following IMP dosing (parasitaemia not reduced ≥ 10 -fold by Day 10 compared with peak parasitaemia on Day 8).
- Parasite regrowth following IMP dosing (initial parasite clearance is followed by asexual parasite regrowth above 5000 parasites/mL).

- Participant discontinuation/withdrawal (see Section 7).
- Investigator's discretion in the interest of participant safety.

The following procedures will be performed prior to antimalarial rescue treatment:

- Obtain malaria clinical score.
- Record vital signs.
- Record AEs and use of concomitant medications.
- Check participant diary cards.
- Perform symptom-directed physical examination if clinically indicated.
- Collect blood samples for:
 - malaria PCR,
 - parasite *ex vivo* viability (only in the event of parasite regrowth),
 - parasite drug resistance (only in the event of parasite regrowth).

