#### 4. STATISTICAL CONSIDERATIONS

Data analysis will be performed according to the Sponsor's representative Standard Operating Procedures (SOPs).

The general analytical approach for all endpoints will be descriptive in nature. All summaries will present the data by dose group as well as by all participants combined.

Unless otherwise stated, the following statistical approaches will be taken:

Continuous variables:	Descriptive statistics will include the number of non-missing values, mean, standard deviation (SD), CV%, median, interquartile range, minimum, and maximum. The minimum and maximum values will be presented to the same number of decimal places as recorded in the raw data; mean and median will be presented to 1 decimal place more than raw data; and SD will be presented to two more decimal places than the raw data. The number of decimals for lab parameters may be reduced if the full presentation of the data includes more than 4 significant figures.
Categorical variables:	Descriptive statistics will include frequency counts and percentages per category. Percentages will be rounded to one decimal place, with the denominator being the number of patients in the relevant population.
Imputation:	No imputation will be performed for missing data.
Confidence intervals (CIs):	CIs will be two-sided and will use 95% confidence levels.
Unscheduled Visits	Unscheduled visits that do not have laboratory data on the same visit date will be excluded from summary tables.
Early termination visit	Assessments conducted at Early Termination will be excluded from visit-based summary tables unless otherwise indicated.

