##### ***Biostatistical methods***

ECG parameters will be listed for all participants and visits. Triplicate ECGs will be presented in listings for individual readings as well as the mean for each triplicate. The triplicate means will be used for the summary table. Any values outside of the protocol defined normal ranges (Table XX) will be flagged.

*Table 2: ECG Normal Ranges*

Parameter	Range
PR interval	≤210 msec
QRS	50–120 msec
QTcF	Males: ≤450 msec Females: ≤470 msec

Observed values, as well as changes from treatment baseline, will be summarised descriptively for all ECG parameters by visit. An addition table will present the frequencies of participants who fulfill the following prolongation (change from baseline) criteria, considering all scheduled and non-scheduled visit data:

- QTcF prolongation >30
- QTcF prolongation >60
- QTcF >450 msec for males
- QTcF >450 msec for females
- QTcF >470 msec for females

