#### **11.3.8. Malaria Clinical Score**

Malaria clinical score data will be listed for all participants, including the individual scores for each of the 14 signs/symptoms as well as the total score.

The number (and percentage) of participants scoring each symptom (0=absent; 1=mild; 2=moderate; 3=severe) will be tabulated per dose group and per protocol defined timepoint.

The highest score as well as the time(s) to the highest score observed will be tabulated.

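### The peak malaria clinical score table has no exception to the rule that drops unscheduled visits, so a peak recorded at a symptom-driven extra visit can be left out

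*SAP*

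**What the plan says.** SAP section 4 introduces its general rules with "Unless otherwise stated, the following statistical approaches will be taken", so each is a default that a later section may override. The rule on unscheduled visits reads: "Unscheduled visits that do not have laboratory data on the same visit date will be excluded from summary tables". The next row, on early termination, is narrower: "Assessments conducted at Early Termination will be excluded from visit-based summary tables unless otherwise indicated".

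Protocol 9.4.1 has no laboratory condition and no by-visit limit: "Unscheduled visits will be excluded from summary tables", and "Assessments conducted at Early Termination will be excluded from summary tables". SAP section 13 nevertheless reports no change to the planned analysis.

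On the score itself, SAP 11.3.8 first tabulates symptom grades by planned timepoint and then adds: "The highest score as well as the time(s) to the highest score observed will be tabulated". SAP Table B lists the peak and time to peak as a summary table in the Full Analysis Set, and separately lists a table of abnormal vital signs. Neither has a stated exception for unscheduled visits. SAP 11.3.7 gives one for the QTcF categories: "considering all scheduled and non-scheduled visit data".

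**The concern.** A peak is a worst-value measure, so it should be taken over everything that was observed. Protocol 8.2 allows safety assessments at unscheduled visits when safety requires them, and Protocol 12.1.6 allows more frequent follow-up when clinically indicated. Visits of this kind are prompted by how the participant is doing. Removing them from a maximum is therefore not neutral in the way that removing them from a by-visit mean is.

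Under the SAP wording, whether such a score counts depends on whether a laboratory sample was taken that day, which is not a measure of severity. The malaria clinical score is the named measure of the severity of induced infection within the second secondary safety endpoint, and dose groups are very small, so one omitted peak can change a group's summary.

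**Working it through.** The plan gives no figure for this table (no power, margin or expected score), so there is nothing to reproduce. The check is of the text, followed by bounding arithmetic.

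**1. Which rule reaches which table**

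| Assessment | SAP 4 | Protocol 9.4.1 |
|---|---|---|
| Score or vital signs at an extra visit, no sample taken | Dropped | Dropped |
| Score or vital signs at an extra visit with same-day laboratory data | Kept | Dropped |
| Laboratory abnormality at an extra visit | Kept (it is itself laboratory data) | Dropped |
| Early-termination score, peak table | Kept (not a visit-based table) | Dropped |

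The two documents can therefore give different peak tables from the same data.

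**2. The early definitive-treatment visit for regrowth**

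Protocol 12.1.7 introduces its list with "The following procedures will be performed prior to antimalarial rescue treatment". The list includes the clinical score, vital signs and malaria PCR and, if there is regrowth, *ex vivo* viability and drug resistance samples. It does not include haematology or biochemistry. Under SAP 4 the score is lost only if two conditions both hold: the visit is classed as unscheduled, and laboratory data means safety haematology or biochemistry alone. Neither is settled. SAP 4 does not define the term. SAP 4.1.2.3 treats the PCR source as a laboratory, while the parameter list in SAP 11.3.3 omits PCR. Under Protocol 9.4.1 the first condition alone is enough.

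**3. Can a peak fall between scheduled scores?**

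The schedules of activities give 23 scheduled scores per participant:
- 5 before admission: Days 0, 4, 5, 6 and 7 AM.
- 10 in confinement: pre-dose, then 6, 12, 24, 30, 36, 48, 54, 60 and 72 h.
- 8 as outpatient: Days 12, 13, 15, 17, 20, 22, 24 and 27.

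After dosing, gaps exceed 24 h only from Day 13: 48 h for Days 13–15, 15–17, 20–22 and 22–24, and 72 h for Days 17–20 and 24–27. Protocol 4.3 predicts return to baseline parasitaemia at 20 mg at a median of 7 days after dosing (95% CI 2.5 to 14). With dosing on Day 8 this is Day 15 (Day 10.5 to Day 22). So the wider gaps overlap the later part of that range, and scoring is dense in the earlier part.

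**4. Direction**

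The maximum over a subset of visits cannot exceed the maximum over all visits. The peak can only be unchanged or too low. The time to peak can move either way.

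**5. Size, under stated assumptions**

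If one participant in a group of n has a tabulated peak d points too low, the group mean falls by d / n. The documents give no d; 1 to 10 points on the 0–42 scale is assumed.

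| n | d = 1 | d = 10 |
|---|---|---|
| 1 (Cohort 1, 1500 mg) | 1.00 | 10.00 |
| 2 (Cohort 1, 90 mg) | 0.50 | 5.00 |
| 3 (Cohort 1, 20 mg) | 0.33 | 3.33 |
| 18 (maximum enrolment) | 0.06 | 0.56 |

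If no peak falls at an excluded visit, every entry is zero.

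**The case against.** The strongest reply is that SAP 11.3.8 already separates the two outputs. Grades are tied to planned timepoints, while the next sentence speaks of the highest score observed with no such limit, and SAP 4 yields to later sections. That reading is reasonable but not secure. The QTcF section needed explicit words to bring in unscheduled data, and the row on early termination shows that the authors knew how to limit an exclusion to visit-based tables. The row on unscheduled visits has no such limit. At best the override is ambiguous.

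A second reply is that severity stays visible elsewhere. SAP 11.3.8 lists all scores for all participants, and SAP 11.3.1 summarises adverse events by maximum severity with no visit filter stated. Protocol 9.4.4 promises only the listing of scores. This is true, and it limits the harm, but neither output corrects a tabulated peak total score or time to peak.

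A third reply concerns opportunity. Scores are frequent through Day 13. From Day 15 the ±24 h windows in Protocol 8.2 for vital signs and blood samples touch every day to Day 28, so some extra visits might be mapped to a scheduled one. This makes exclusion less frequent but does not rule it out, because each window holds one scheduled visit.

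A reader might go further and infer that regrowth visits are routinely lost, that they are the likeliest place for the peak, or that laboratory abnormality tables suffer in the same way. The documents do not support these readings. The regrowth visit carries samples that may count as laboratory data. Its treatment threshold, 5000 parasites/mL, is the level that Protocol 4.2 expects to be exceeded on Day 8 with symptoms absent or at most moderate. The SAP rule cannot remove a laboratory result.

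**Conclusion.** The point holds as a gap in specification. As written, SAP 4 can drop a score from the peak table, and a reading from the abnormal vital signs table, when it was taken at an extra visit without laboratory data. Protocol 9.4.1 would drop it from any extra visit. Laboratory abnormality tables are affected only under the protocol wording.

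The peak can be understated and the time to peak shifted. It does not follow that they will be: this needs a participant whose highest score falls at an excluded visit, and the documents give no frequency for that. The sizes above rest on one affected participant and an assumed loss of 1 to 10 points. The matter is worth correcting because any error in the peak runs in one direction, groups are as small as one to three in Cohort 1, and the two documents disagree.

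**What to change.** - In SAP 11.3.8, and for the abnormal vital signs table, state that worst-value summaries use all post-inoculation assessments, including unscheduled, pre-treatment and early-termination visits, in line with what SAP 11.3.7 does for QTcF.
- In SAP 4, limit the exclusion of unscheduled visits to by-visit summaries. If the laboratory condition is kept there, define laboratory data and say how an early definitive-treatment visit is classed.
- Reconcile SAP 4 with Protocol 9.4.1 for both unscheduled and early-termination visits, or record the difference in SAP section 13. This also settles the laboratory abnormality tables.

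The cost is a few lines of SAP text and minor programming. No new data are needed, since the scores are already due to be collected and listed. Reported peak scores may become slightly less favourable.

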#### 4.1 Data Capture

##### 4.1.1 Database

The primary method of data collection is via the study database, developed within the chosen Electronic Data Capture (EDC) platform, IBM Clinical Development. The database has been designed based on the final protocol, the system/core configuration, electronic Case Report Form (eCRF) specifications and/or mock eCRF and consistency check specifications.

Data will be entered directly into the EDC system. Site-collected data will be entered directly from source notes at the site and will be verified by Clinical Research Associates (CRAs) to ensure data integrity.

Refer to the Data Management Plan for further details.

##### 4.1.2. Third Party Data

###### 4.1.2.1 Safety Laboratory

Central safety laboratory data will be received from Sullivan Nicolaides (SNP) Pathology Central Laboratory as specified in the Data Transfer Specification. At least one transfer will be delivered prior to database lock and reconciled against CRF data. Following successful reconciliation and resolution of any data issues, the data will be incorporated into the End of Study analysis.

No unit conversion of laboratory data will be performed.

#### **4.1.2.2 PK Laboratory**

PK samples will be analysed by Swiss BioQuant Central (SBQ) and PK parameters will be derived by PharmaKinetic. Final PK assay data will be transferred to SSR, as specified in the SBQ DTS, for incorporation into the PC SDTM.

#### **4.1.2.3 PD Laboratory**

All parasitaemia data will be generated by the Queensland Paediatric Infectious Diseases (QPID) laboratory and captured electronically using MARS (18S qPCR parasitaemia data). All parasite life-stage data (i.e. gametocytæmia and ring-stage parasites) will be generated by the QPID laboratory and transferred electronically to the Queensland Institute of Medical Research (QIMR) Berghofer and this data will be used for PK/PD modelling. QIMR will provide the 'raw' PCR data 18S, the female gametocyte-specific transcript (pfs25), the male gametocyte-specific transcript (pfMGET) and the ring-stage transcript (pfSBP-1) to SSR as per DTS, and final PD parameters will be in the PRR report.

#### **4.1.2.4 PK/PD Laboratory**

PK/PD analysis will be performed by MMV, Pharmacometrics. SSR will be required to provide the PK concentration and parasitemia data, as well as any CRF datasets required to perform the PK/PD analyses (e.g. demographics, drug administration data).

### **4.2 Statistical Programming**

#### **4.2.1 Programming Specifications**

##### **4.2.1.1 Safety Analysis**

Programming specifications will be prepared to detail the SAS programming of CDISC (SDTM and ADaM) datasets and listings, tables and figures.

##### **4.2.1.2 PD Analysis**

Data manipulation and data analyses for all PD data will be performed using R (version 4.1.0 or higher).

##### **4.2.1.3 PK Analysis**

The estimation of pharmacokinetic parameters by non-compartmental analysis (NCA) methods will be performed using Phoenix WinNonlin software (v8.3 or a more recent version, Certara USA, Inc., USA).

##### **4.2.1.4 PKPD Analysis**

All data processing, analysis, model setup and modeling result analysis including goodness-of-fit plots will be performed using R 3.6.3 or above and IQRtools package 1.8.0 or above.

NLME modelling will be performed with Monolix 2019R1 [MLX19] using Stochastic Approximation Expectation Maximization (SAEM) for parameter estimation. For PD modelling where typically the variance of random-effects cannot be estimated from the data, the IQRtools SysFit approach will be used to estimate typical and individual PD parameters.

#### 4.2.2 **Baseline**

Baseline will be defined as:

##### Safety

- The last scheduled observation prior to the administration of the malaria challenge inoculum [Inoculation Baseline],
- The last scheduled observation prior to the first administration of IMP [Treatment Baseline].

For replicate measurements (e.g., ECG) at baseline, the mean of those replicates will be used as the baseline value.

##### PD

- The last observation prior to the administration of the IMP for PD data.

##### PK

- The last observation prior to the administration of the IMP for PK data.

#### 4.2.3 **Change from Baseline**

Change from Baseline will be calculated as:

$$\text{Change from baseline} = (\text{postbaseline value}) - \text{baseline value}$$

##### 4.2.3.1 **Days relative to Inoculation**

$$\text{Days} = (\text{Assessment Date} - \text{Inoculation Administration Date}) + 1$$

##### 4.2.3.2 **Days relative to IMP administration**

$$\text{Days} = (\text{Assessment Date} - \text{First Study Drug Administration Date}) + 1$$

#### 4.2.4 **IMP Treatment Groups**

Tabulations will summarise data by the IMP dose groups and these may vary for each cohort.

### 5. ANALYSIS SETS

The analysis sets to be used for the analyses will be: Full Analyses set (FAS), IMP set, PK set, PD set and PK/PD set.

The number of participants in each analysis set will be summarised, with a corresponding listing.

#### 5.1 Analysis Set Descriptions

##### 5.1.1 **Full Analysis Set**

The Full Analysis Set (FAS) will consist of all enrolled participants, i.e. participants that received the malaria challenge agent.

#### **5.1.2 *IMP Set***

The IMP Set will include all enrolled participants administered with the IMP.

#### **5.1.3 *PK Analysis Set***

The PK analysis set will include all participants who have sufficient plasma samples taken for at least one of the PK parameters to be calculated and who received any study treatment and experienced no protocol deviations with relevant impact on PK data. Should an adverse event, for example, vomiting within 4 hours of IMP dosing occur and be deemed detrimental to the data quality, additional subsets may be invoked, and those participants be omitted from the summary statistics. This will be confirmed by the sponsor if applicable.

#### **5.1.4 *PD Analysis Set***

The PD analysis set will include all participants inoculated with the malaria challenge agent and who develop parasitaemia detectable by qPCR, received a dose of MMV367, and have no protocol deviations that would exclude them from the PD analysis due to their impact on the PD analysis.

#### **5.1.5 *PK/PD Analysis Set***

The PK/PD analysis set will include all participants included in both the PK set and the PD set.

### **6. PROTOCOL DEVIATIONS**

#### Analysis Set: FAS

All protocol deviations will be listed, grouped by participant and dose group.

The protocol deviation summary table will capture all deviations as minor and major.

The protocol deviation summary table will include:

- The total number of minor protocol deviations
- The total number of major protocol deviations
- The number of Participants who reported at least one minor protocol deviation
- The number of Participants who reported at least one major protocol deviation

## 7. PARTICIPANT DISPOSITION

Analysis Set: FAS

### 7.1 Disposition

A listing of participant disposition will present:

- Date of informed consent
- Date of inoculation
- Date of IMP administration
- Date of mandatory rescue medication administration
- Date of Primacin administration when applicable
- Did the participant complete the study?
- Date of completion / early withdrawal
- Primary reason for early withdrawal (including instances where early termination was related to COVID-19)

Detailed early withdrawal information will also be listed in a separate listing.

If there are any deaths reported, a separate death listing will be prepared.

The number and percentage of Participants entering and discontinuing the study will be summarised by dose group and overall along with the reason for discontinuation. The participant disposition summary table will include:

- Number of participants signed informed consent
- Number of participants who received IMP
- Number of participants who completed the full study
- Number of participants withdrawn from the study early
- Reason for early withdrawal

### 7.2 Analysis of Population Assignment

Analysis set data will be listed for all participants. A summary table will show the number of participants within each of the analysis sets.

## 8. DEMOGRAPHIC AND BASELINE INFORMATION

Analysis Set: FAS

### 8.1 Demographics

Demographic data will be listed for all enrolled participants and summarised by dose group and overall. Data includes:

Age  
Sex  
Women of Child-bearing potential  
Post-menopausal women  
Race  
Ethnicity  
Weight (kg)  
Height (m)  
BMI (kg/m^2)

### 8.2 Medical History

All medical history data will be listed, grouped by participant.

Medical history will be coded using the Medical Dictionary for Regulatory Activities (MedDRA version 24.1) and summarised by system organ class (SOC) and preferred term (PT).

### **8.3 Prior Medications**

Prior medications are defined as any medication that is started before first inoculation with the malaria challenge agent, regardless of when it ended. If a medication has a missing or partial missing start/end date or time and it cannot be determined whether it was taken before IMP or concomitantly, it will be considered as prior and concomitant. Medications will be coded using WHO Drug Dictionary September 2021 release.

Prior medications will be listed.

### **8.4 Drug Screen**

Drug screen data will be listed for all participants.

### **8.5 Alcohol Screen**

Alcohol screening data will be listed for all participants.

### **8.6 SARS-CoV-2 Screening**

Any positive SARS-CoV2 screening results will be listed.

### **8.7 Follicle Stimulating Hormone (FSH)**

FSH results will be listed for Post-menopausal women only.

### **8.8 Beck Depression Inventory**

Beck Depression Inventory (BDI-II) data will be listed for all participants, including answers to the individual questions as well as the total scores, which are auto-calculated within the CRF.

